## Introduction

Depression is a widespread mental health disorder estimated to affect around 3.8% of the global, adult population to various degrees (1). In Denmark, data suggest an overall prevalence of depression of 4.1% with moderate to severe depression comprising 3% (2).

Major depression is linked to various negative health outcomes such as diminished quality of life and medical morbidity and mortality (3, 4). In 2014, depression was ranked by The World Health Organization (WHO) as the fourth leading cause of disability worldwide, and it was, at the time, estimated that by 2020, depression would be the second leading cause of disability globally (3). This was later supported by a large study in 2021, The Global Burden of Diseases, Injuries, and Risk Factors Study 2021(GBD 2021) (3, 5). The study aimed to quantify health loss and the burden of disease across places and over time, and the analysis estimated “years lived with disability” (YLDs) for 371 diseases and injuries in 204 countries from 1990 to 2021. Among the top three causes of YLDs (across all ages and sexes combined), depressive disorders were the second leading cause with approximately 56 million YLDs (5). They observed the largest increase in age-standardised YLD rates, between 2010 and 2021, in depressive disorders, as well as diabetes, anxiety disorders, drug use disorders and neonatal disorders (5).

Furthermore, it is well established that depression can lead to symptoms that impact the individual’s ability to perform in the workplace, such as lack of concentration, fatigue, decreased motivation and job performance, but also diminished sense of self-worth and confidence (6). The cost of depression is not only on the level of the individual, but also on a societal level (7). It has been estimated that, in the United States alone, the total economic cost of depression in 2000 was over US\$83 billion, with workplace costs (i.e., absenteeism and presenteeism) accounting for US\$51.5 billion of the total (6). By 2017, the total cost of depression in the USA had risen to an estimated US\$210 billion (8). From both an economic and an ethical point of view, the need for optimised and effective treatment approaches for depression is crucial.

In Denmark, treatment for depression most often consists of medication, psychotherapy, or a combination of both, and the treatment is facilitated through four main settings: general practitioners, psychologists, psychiatrists in private practice, or hospital-based psychiatry.

General practitioners act as gatekeepers to hospital-based psychiatry, meaning that a large proportion of individuals experiencing a depressive episode are primarily seen and treated in general practice.

Studies from general practice have shown that, on average, about 10% of all contacts with general practitioners can be attributed to depressive disorders, and that depression is highly underdiagnosed in general practice, with fewer than half of the cases being identified (9).

Treatment of depressive disorder is challenging, with up to 40% of patients not responding to the initial medication prescribed, and often several trials of different treatments are required to achieve symptomatic remission (7, 10-12). Remission often occurs within four to six weeks after treatment has been initiated. However, there is often a delay between recognising that a treatment is ineffective and making changes to the treatment strategy, thereby prolonging the overall time to remission and resulting in longer duration of depressive symptoms for the patient (7). These findings stress the importance of accurate and timely diagnosis and treatment of individuals with depression.

Algorithm-based treatment offers a means of reducing this impediment, resulting in more efficient treatment for depression. Several studies have shown that algorithm-based treatment of depressive episodes is more effective than treatment as usual (TAU), by reducing time to remission, entailing fewer changes in medication and producing better outcomes as well as a greater reduction in symptoms (4, 7, 10, 12-14).

Results from the *Randomized Controlled Multicentre German Algorithm Project3 Trial* (GAP3) showed a significantly reduced time to remission for patients with depression in the group randomised to algorithm-based treatment, compared with the group randomised to treatment as usual (TAU) (10). Additionally, a structured algorithm-guided treatment was associated with fewer medication changes to achieve remission compared to the TAU group (10).

The Texas Medication Algorithm Project (TMAP) found that an algorithm-based approach to the treatment of major depressive disorder (MDD) was associated with a statistically and clinically better outcome for participants, in terms of the primary and most of the secondary efficacy assessments, compared with patients in the TAU group (15).

An Algorithm-based treatment approach consists of key elements, such as strategies and treatment steps, that determine which treatments to use, when to use them, how to implement

them and in which order. Another essential element is the use of critical decision points (CDPs), at which time the response to the current treatment is assessed. This assessment leads to specific, predefined adjustments to the current treatment (e.g. to continue the current treatment or change treatment choice according to a predetermined plan) applying preset “if-then-rules”, meaning that “if X happens, then Y will happen” (13). Most often, measurement-based care is implemented to assess treatment effects, meaning that a symptom, outcome, or process measure is administered routinely, e.g. a rating scale (16, 17). The structured treatment plan will also define the interval between the critical decision points, thereby determining how long a specific treatment is maintained and when to revise it.

A systematic approach to treatment of depression could enhance patient outcomes and improve the quality of care, while also ensuring personalised care and accommodating individual differences among patients, potentially leading to a decrease in the costs of health care (14).

As previously mentioned, treatment for depression is most often based on either pharmacological treatment, psychotherapy — often facilitated by a psychologist — or a combination of both. Medication plays a crucial role in treating depression, and selective serotonin reuptake inhibitors (SSRIs) are commonly prescribed antidepressants that have demonstrated efficacy in alleviating depressive symptoms and are generally well tolerated (8). These are often prescribed by general practitioners as a first-line treatment for depression. Collaboration between general practitioners and psychologists is essential in providing comprehensive care for individuals with depression. In general practice, patients can be referred to a psychologist for psychotherapy to address underlying psychological factors and to develop coping strategies.

One of the most well-documented types of psychological interventions is cognitive behavioural therapy (CBT), which is recommended in most treatment guidelines (18). Previous studies have shown a significant efficacy when it comes to psychological interventions such as cognitive behavioural therapy (CBT) in the treatment of depression. However, a recent meta-analysis including 409 trials with over 52.000 patients, examined the effect and efficacy of CBT compared with other psychotherapies and pharmacotherapies (18). They concluded that the

efficacy of CBT for depression is documented across different formats, age groups, target groups, and settings, but that the superiority of CBT over other psychotherapies for depression did not emerge clearly from the analysis. On the other hand, the findings suggested that CBT was as effective as pharmacotherapy in the short term and more effective in the long term. Another meta-analysis investigated the relative efficacy of psychotherapy against combined therapy (i.e. psychotherapy with pharmacotherapy) (19). Combined therapy was more efficacious than psychotherapy alone, however, the results depended on the severity and chronicity of the depressive disorder. No differences in the outcome were observed when comparing mild and moderate non-chronic depressive episodes, indicating that psychotherapy alone had the equivalent efficacy as psychotherapy and pharmacotherapy combined in these patients.

Studies on algorithm-based treatment and its efficacy have primarily focused on either hospitalised patients (inpatients) or those receiving treatment in an outpatient clinic (outpatients). In Denmark, most individuals with depressive episodes are treated in general practice and not as in- or outpatients.

Since studies show a significantly better outcome compared to treatment as usual, it is plausible to think that this also applies to patients treated for depression in general practice. If proven to be true, the results of this study could potentially lead to changes in the management and treatment of patients with depressive disorder in general practice, resulting in a more efficient treatment strategy with several benefits — both for the individual patient and from a societal perspective — including improved quality of life, reduced morbidity and mortality, and lower economic costs for society in general.

Additionally, the study aims to identify, through direct comparison, whether treatment provided by a general practitioner, both TAU and algorithm-based, is superior to treatment as usual (psychotherapy in the form of CBT) provided by a psychologist.

To our knowledge, no such study has been conducted to date.

## Aim of the study

The purpose of this study is to investigate the effectiveness of three different treatment pathways for moderate depressive episodes as part of unipolar depressive disorder, through a three-armed, open-label randomised controlled study. Participants will be allocated to one of the three groups in a 1:1:1 ratio.

The three treatment pathways will be as following:

1. Treatment as usual by a general practitioner (TAU-GP).
2. Treatment as usual by a psychologist (TAU-P).
3. An algorithm-based pharmacological treatment by a general practitioner (ALGO).

The primary outcome of the study is to examine whether there is a difference between the three groups. It will be measured by using a F-test from baseline to end of study at 12 weeks, using the Hamilton Depression Scale, 6 item version (HAM-D6).

Additionally, several secondary outcomes will be explored, e.g. the difference in differences (DID) between TAU-GP vs. ALGO, TAU-GP vs. TAU-P and TAU-P vs. ALGO.

The hypothesis is that a tailored algorithm-based treatment regarding patients with depression, treated in general practice, is more effective than treatment as usual (TAU), whether provided by general practitioners (GPs) or psychologists.

Furthermore, a qualitative study will be conducted to investigate the impact of the assigned treatment pathway from the participant's perspectives.

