### Secondary outcomes

All secondary outcomes are based on the mITT population unless otherwise specified. The following secondary outcomes will be explored:

- The difference in differences (DID) in HAM-D6 score, from baseline to end of study, between participants in:
  1. TAU-GP and ALGO
  2. TAU-GP-and TAU-P
  3. TAU-P and ALGO
- The DID in C-SSRS score, from baseline to end of study, between participants in:
  1. TAU-GP and ALGO
  2. TAU-GP-and TAU-P
  3. TAU-P and ALGO
- The DID in MDI score, from baseline to end of study, between participants in:
  1. TAU-GP and ALGO
  2. TAU-GP-and TAU-P
  3. TAU-P and ALGO
- The DID in PSP score, from baseline to end of study, between participants in:
  1. TAU-GP and ALGO
  2. TAU-GP-and TAU-P
  3. TAU-P and ALGO
- The impact of the assigned treatment pathway from the participant's point of view and the participant's personal experience of recovery through a self-rating scale (Brief INSPIRE-O). This will also be done using the DID, from baseline to end of study, between participants in:
  1. TAU-GP and ALGO

2. TAU-GP-and TAU-P

3. TAU-P and ALGO

- The concordance between MDI and HAM-D6.
- Duration of sick leave after baseline (indicated in days) within the current depressive episode.
- A Per Protocol analysis at week 12 (PP12) will also be completed for all continuous secondary outcomes.
- A Per Protocol analysis at week 12 (PP12) will also be completed for the primary outcome.
- Between-group difference for adverse events and serious adverse events.
- Between-group difference for the ITT population in reasons for premature discontinuation, time to all-cause discontinuation

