## Statistics and Power Calculation

### Statistics

The difference in HAM-D6 score between baseline and follow up will be compared between the three groups. A F-test will be used to assess if there is a significant difference among the groups. The analysis will be applied to the mITT population using last-observation-carried-forward (LOCF).

The three different treatment groups will be directly compared to each other, i.e. TAU-GP against ALGO, TAU-GP against TAU-P and TAU-P against ALGO. The groups will be compared based on the change in HAM-D6 scores from baseline to endpoint using a two-sided t-test (difference-in-differences [DID] analysis), along with other relevant secondary outcomes.

The DID-analysis will be applied to the mITT population at 12 weeks using LOCF, and the PP12 population.

In secondary analysis, differences between treatment groups regarding changes during the study period for each of the HAM-D6, MDI, PSP, C-SSRS, and Brief INSPIRE-O scores, will be analysed in separate mixed effects models. The models will be analysed with the relevant outcome as dependent variable, and time, treatment, and their interaction as fixed effects as well as patient and centre as random effects, also using the mITT and PP12 populations.

The proportion of responders (defined as a 50% reduction of HAM-D6 score) or remitters (defined as a HAM-D6 score  $\leq 5$ ) will be compared between the three groups, using chi-square tests for association and/or Poisson regression with a robust estimation of the standard error. The same will be applied to the remaining categorical variables. The analyses will be performed by using the mITT population. A similar analysis will be carried out for the categorical variable reasons for treatment discontinuation in the ITT population.

Further, risk of adverse events and serious adverse events is compared by applying Poisson regression with a robust estimation of the standard error in the mITT population.

To investigate the differences in time to all-cause discontinuation and duration of sick leave after baseline between the three groups, compared two and two, the time in the study will be compared by applying a two-sided t-test. Analysis of sick leave days is carried out on the mITT population and time to all-cause discontinuation will be performed on the ITT population.

Concordance between HAM-D6 and MDI will be analysed visually.

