Exploratory analyses will extend the primary linear mixed-effects model by adding baseline variables (age, sex, educational level, baseline HAM-D6, duration of untreated depression, age at first episode, psychiatric/physical comorbidity, prior treatment history and DART score). If deemed feasible, non-linear dynamics as the interaction with treatment arm or an estimation using splines will be included. Relevant effects will be reported as regression coefficients or odds ratios with 95 % CIs and visualised in stratified plots where relevant.

All model assumptions are checked visually and sensitivity analyses, using bootstrap to estimate standard errors, are conducted in case of any violations.

All secondary outcomes will be analysed regardless of the significance of the primary outcome.

The statistical analyses will be performed by a statistician at the Department of Psychiatric Research, Aalborg University Hospital, Psychiatry, using Stata 19.

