#### Power calculation

To detect a clinically relevant difference of at least 2.25 points of HAM-D6, with a power of 0.80 and a significance level of 0.05 (two-sided), 45 patients are required in each of the three groups (27, 28). To further account for an estimated dropout of 20%, a total of 57 patients are needed in each group.

The standard deviation of the difference in HAM-D6 between baseline and 12 weeks of treatment is assumed to be equal to 3.9 in all three groups (29).

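### Does an omnibus F-test as the only primary test leave the hypothesis that the algorithm arm beats usual care without a test?

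*Protocol*

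**What the plan says.** The Protocol's Aim of the study section holds both halves of the point. The primary question is non-directional: "The primary outcome of the study is to examine whether there is a difference between the three groups". The hypothesis is directional. It expects that algorithm-based treatment "is more effective than treatment as usual (TAU), whether provided by general practitioners (GPs) or psychologists". The pairwise comparisons are placed below the primary: "several secondary outcomes will be explored, e.g. the difference in differences (DID) between TAU-GP vs. ALGO", followed by the other two pairs.

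The Statistics section repeats the primary test: "A F-test will be used to assess if there is a significant difference among the groups". It then gives each of the three pairs a two-sided t-test on HAM-D6 change to week 12, in the modified intention-to-treat set with last observation carried forward, and again in the week-12 completers. The Secondary outcomes section lists the same pairs under "The difference in differences (DID) in HAM-D6 score, from baseline to end of study, between participants in". The Statistics section ends with "All secondary outcomes will be analysed regardless of the significance of the primary outcome".

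The Introduction adds a further question, to be settled by direct comparison: "whether treatment provided by a general practitioner, both TAU and algorithm-based, is superior to treatment as usual" by a psychologist. The Power calculation gives its target as "To detect a clinically relevant difference of at least 2.25 points of HAM-D6" and names no pair of arms.

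**The concern.** The hypothesis names an arm and a direction, and the primary test has neither. The F-test is as likely to be significant when ALGO is the worst arm as when it is the best. The contrasts that could settle the matter are secondary, and nothing in the protocol says whether the hypothesis needs a win over both usual-care arms, over either one, or over their average. These readings can give different answers from the same data. In an open-label trial one would rather see that settled in advance. At stake is whether a positive primary result could be presented as proof that ALGO is superior, and whether the trial has the power for such a claim.

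**Working it through.** **Inputs.** Difference 2.25, SD of change 3.9 in every arm, two-sided 0.05, power 0.80, 45 per arm before and 57 after 20% dropout (Protocol, Power calculation); 171 in total (Study population); 1:1:1 allocation (Aim of the study). The protocol does not say where the third arm's mean lies, so that is an assumption here. Change scores are taken as normal.

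**Step 1: reproduce the sample size.** For the F-test, noncentrality = n × Σ(mean − grand mean)² / SD². With arm means 0, 0 and 2.25 the grand mean is 0.75 and the sum of squares is 0.5625 + 0.5625 + 2.25 = 3.375.

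- n = 45: 45 × 3.375 / 15.21 = 9.99 on 2 and 132 df; power 80.5%. With 44 it is 79.6%, so 45 is the smallest adequate n.
- n = 57: 57 × 3.375 / 15.21 = 12.65; power 89.4%.
- Dropout: 45 / 0.8 = 56.25, rounded up to 57; 3 × 57 = 171.

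A two-sample t-test would need 49 per arm, and an F-test with the third arm midway would need 59. The stated figure is therefore the F-test figure with one arm apart from two equal ones.

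**Step 2: what the F-test can show.** The noncentrality uses squared deviations, so it is the same whichever arm stands apart and in either direction. A significant result supports only that the arms differ.

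**Step 3: what the contrasts show.** For one pair at n = 45, 2.25 / (3.9 × √(2/45)) = 2.25 / 0.822 = 2.74 on 88 df; power 77.2%. At n = 57 it is 86.3%. The joint results come from simulation with at least 200,000 trials per scenario. The table gives the percentage of trials at 45 analysed per arm, with 57 in brackets; a win is a two-sided p below 0.05 in ALGO's favour.

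| True state | F significant | ALGO beats TAU-GP | ALGO beats TAU-P | At least one | Both |
|---|---|---|---|---|---|
| ALGO 2.25 better than both | 80.5 (89.4) | 77 (86) | 77 (86) | 90 (95) | 65 (78) |
| ALGO equal to TAU-GP, TAU-P 2.25 worse | 80.5 (89.4) | 2.5 (2.5) | 77 (86) | 77 (86) | 2.5 (2.5) |
| ALGO 2.25 worse than both | 80.5 (89.4) | 0 | 0 | 0 | 0 |
| No difference | 5 | 2.5 | 2.5 | 4.5 | 0.5 |

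Against the average of the two usual-care arms, the standard error at n = 45 is 3.9 × √(1.5/45) = 0.712. Power is then 88% (94%) in the first row and 35% (42%) in the second, where the true contrast is 1.125.

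**Step 4: read the second row.** The F-test is significant in four trials out of five although ALGO does not beat usual care by GPs. But ALGO really is 2.25 better than TAU-P there, and the contrast with TAU-P finds it in 77% of trials, while the contrast with TAU-GP is significant in ALGO's favour in only 2.5%. Both contrasts are reported, so a reader sees a win over one arm and not the other. The 77% is almost all correct detection, not false success.

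**Step 5: error of the natural reading.** The hypothesis names GPs and psychologists as alternative providers of the comparator, which most naturally means that ALGO should beat each. If ALGO is no better than one of them, that contrast favours ALGO significantly in at most 2.5% of trials, so a win on both is false in at most 2.5%. No split of alpha is needed.

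**The case for a change.** The best case for a change is that it costs one sentence and no patients. The protocol could say that a significant F-test alone does not confirm the hypothesis and that both ALGO contrasts must succeed. When ALGO is truly 2.25 better than both arms, the F-test is significant without both contrasts in 16% of trials at 45 per arm (12% at 57). Power for the joint win at 45 is about 65%, below the 80% a reader may assume. With no true difference, at least one of the three unadjusted pairs is significant in 12.2% of trials.

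Part of this stands. A significant F-test does not establish the hypothesis, and the protocol does not say in so many words which contrasts do.

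The rest does not carry a change. No sentence treats a significant F-test as confirming ALGO, and the Power calculation promises nothing for the pairs. The 12.2% concerns any pair in any direction, not the ALGO claim: both ALGO contrasts succeed by chance in about 0.5% of trials. Nor can one say that the rule will be picked once the data are known, because the analysis plan may already hold it. The Introduction's question is less open than it seems: it calls for direct comparison, the term that the Statistics section uses for the pairwise tests.

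**Conclusion.** No change is needed. Followed as written, the plan gives a valid F-test for the stated primary objective, a sample size that is correct for that test, and separately reported, signed ALGO contrasts that answer the directional hypothesis. A directional expectation beside a non-directional primary test is common and is not a contradiction. The gap is one interpretive sentence, which analysts would fill sensibly: the F-test supports a difference among arms, and the two ALGO contrasts bear on the hypothesis.

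Choosing among a win on both contrasts, a contrast with the average, or a requirement that the F-test also be significant is a trade-off for the authors. Making the joint win a formal criterion would turn contrasts now labelled secondary into a confirmatory claim with about 65% power at 45 analysed per arm (78% at 57), which the protocol does not currently make.

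The power figures assume SD 3.9 in every arm, a true difference of 2.25 and two equal usual-care arms. With the third arm midway, F-test power falls to 68% at 45 per arm. The 2.5% limit on a false joint claim does not depend on where the means lie.
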